4.1. Primary Objective

Study objectives are listed in [Table JAHV.4.1](#).

Estimands (International Conference on Harmonisation [ICH] E9 R1) of the study are defined based on the following 4 attributes:

- The population of interest is patients with juvenile idiopathic arthritis (JIA) who have had an inadequate response or intolerance to treatment with at least 1 other conventional or biologic disease-modifying antirheumatic drug (bDMARD). Analysis populations are defined in Section 6.1.1. The analysis population corresponding to each of the efficacy and health outcome endpoints is specified in [Table JAHV.6.4](#), and [Table JAHV.6.8](#).
- Primary, major secondary, and exploratory endpoints/variables are listed in [Table JAHV.4.1](#), [Table JAHV.4.2](#), and [Table JAHV.4.3](#). A full list of efficacy and health outcome endpoints/variables are given in [Table JAHV.6.4](#), [Table JAHV.6.7](#), and [Table JAHV.6.8](#).
- Population Level Summary: categorical variables will be summarized by proportion and continuous variables will be summarized by average. Details are given in Section 6.7.
- Intercurrent Event(s) Strategy: intercurrent events will be handled by the while-on-treatment strategy and the composite strategy approaches as primary strategies. The hypothetical strategy will also be used in supplementary analysis. Specific statistical methods to be used for handling intercurrent events under different strategies are described in Section 6.3. Statistical methods corresponding to each of the efficacy and health outcome variables are summarized in [Table JAHV.6.4](#) and [Table JAHV.6.8](#).

Table JAHV.4.1. Primary Objective and Endpoint

Objectives	Endpoint

Primary To evaluate the efficacy of baricitinib compared to placebo in children with JIA
	
Time to disease flare (flare defined as worsening of $\geq 30\%$ in at least 3 of the 6 PedACR core criteria for JIA and an improvement of $\geq 30\%$ in no more than 1 of the criteria) from the beginning of the double-blind withdrawal (DBW) period to the end of the DBW period

Abbreviations: JIA = juvenile idiopathic arthritis; PedACR = Pediatric American College of Rheumatology.

4.2. Secondary Objectives

Table JAHV.4.2. Secondary Objectives and Endpoints

Objectives	Endpoints

Secondary
 
 • To evaluate the efficacy of baricitinib in children with JIA 	
During the open-label lead-in (OLLI) period:
 
 • PedACR30/50/70/90/100 response rates • Changes in each of the 6 individual core set components variables of the PedACR Core Set as follows: 
 ○ Number of active joints ○ Number of joints with limited range of motion ○ Physician’s Global Assessment of Disease Activity ○ Parent’s Global Assessment of Patient’s Overall Well-Being ○ Physical function as measured by the Childhood Health Assessment Questionnaire (CHAQ) ○ Acute-phase reactant (high-sensitivity c-reactive protein [hsCRP]) and erythrocyte sedimentation rate (ESR) • Proportion of patients with inactive disease (as defined by Wallace et al. 2011) • Proportion of patients with minimal disease activity (as defined by Consolaro et al. 2012) • Change from baseline in the Physical Summary Score (PhS) and Psychosocial Summary Score (PsS) of the Child Health Questionnaire-Parent Form 50 (CHQ-PF50) • Changes from baseline in caregiver burden as measured by the Parental Impact-Time and Parental Impact-Emotion scales of the CHQ-PF50 • Change from baseline in Juvenile Arthritis Disease Activity Score-27(JADAS27) • Changes from baseline in arthritis-related pain as measured by the CHAQ pain severity Visual Analogue Scale (VAS) item

Secondary Objectives and Endpoints

Objectives	Endpoints

 • To evaluate the efficacy of baricitinib compared to placebo in children with JIA • To assess the efficacy of baricitinib in children with JPsA • To assess the efficacy of baricitinib compared to placebo in children with JPsA • To assess the efficacy of baricitinib in children with ERA or JPsA • To assess the efficacy of baricitinib compared to placebo in children with ERA or JPsA 	
During the DBW period:
 
 • Proportion of patients with disease flare • PedACR30/50/70/90/100 response rates • Changes from baseline in each of the 6 individual components of the PedACR Core Set variables (due to disease flare or completion) as follows: 
 ○ Number of active joints ○ Number of joints with limited range of motion ○ Physician’s Global Assessment of Disease Activity ○ Parent’s Global Assessment of Patient’s Overall Well-Being ○ Physical function as measured by the CHAQ ○ Acute-phase reactant (hsCRP) and ESR • Proportion of patients with inactive disease (as defined by Wallace et al. 2011) • Proportion of patients with minimal disease activity (as defined by Consolaro et al. 2012) • Proportion of patients in remission (as defined by Wallace et al. 2011) • Change from baseline in JADAS-27 • Change from baseline in the PhS and PsS of the CHQ-PF50 • Change from baseline in caregiver burden as measured by the Parental Impact-Time and Parental Impact-Emotion scales of the CHQ-PF50 • Changes from baseline in arthritis-related pain as measured by the CHAQ pain severity VAS item • Change in Psoriatic Area and Severity Index (PASI) score during the OLLI period • Change from baseline in PASI score during the DBW period • Change in Spondyloarthritis Research Consortium of Canada (SPARCC) enthesitis index during the OLLI period • Change in Juvenile Spondyloarthritis Disease Activity Index (JSpADA) during the OLLI period • Change from baseline in SPARCC enthesitis index during the DBW period • Change from baseline in JSpADA during the DBW period

Secondary Objectives and Endpoints

Objectives	Endpoints

 To evaluate the potential effects of baricitinib on the cellular and humoral immune system 	
 Change in immunoglobulin levels and peripheral blood immunophenotyping (including T and B cells, T cell subsets, and NK cells) from baseline and at Week 4, Week 12, and Week 44 Change of IgG titers from pre-vaccination to 4 weeks and 12 weeks post vaccination in patients eligible for vaccination with tetanus, diphtheria, and pertussis (TDaP) and/or pneumococcal conjugate vaccine according to local guidelines

 To characterize baricitinib PK in the JIA population and explore relationships between baricitinib exposure and study endpoints To assess the patient acceptability and palatability of baricitinib tablets and oral suspension To assess the safety of baricitinib compared to placebo in patients with JIA 	
 Population PK of baricitinib in patients with JIA Proportions of patients achieving PedACR30/50/70/90/100 response rates by PK exposure Time to disease flare in patients with JIA by PK exposure Change in JADAS-27 by PK exposure Assessment of tablet or oral suspension product acceptability and palatability during the OLLI period Adverse events including serious adverse events Permanent discontinuation of investigational product Temporary interruption of investigation product

Abbreviations: CHQ-PF50 = Child Health Questionnaire-Parent Form 50; DBW = double-blind withdrawal; ERA = enthesitis-related juvenile idiopathic arthritis; hsCRP = high-sensitivity C-reactive protein; HRQoL = Health-related Quality of Life; IgA = immunoglobulin A; IgG = immunoglobulin G; JIA = juvenile idiopathic arthritis; JADAS = Juvenile Arthritis Disease Activity Score; JPsA = juvenile psoriatic arthritis; NK = natural killer; OLLI = open-label lead-in; PedACR = Pediatric American College of Rheumatology; PK = pharmacokinetic(s); VAS = Visual Analog Scale.

4.3. Exploratory Objectives

Table JAHV.4.3. Exploratory Objectives and Endpoints

[figure not shown]
Objectives	Endpoints

Exploratory
 
 • To evaluate the quality of life (QOL) in children with JIA treated with baricitinib • To evaluate the QOL in children with JIA treated with baricitinib compared to placebo • To evaluate the efficacy of baricitinib compared to placebo in structural joint damage • Describe the skeletal age in pediatric patients 	
 • Change in European Quality of Life-5 Dimensions–Youth version (EQ-5D-Y) scores during the OLLI period • Change from baseline in EQ-5D-Y scores during the DBW period • Change from baseline in the individual scales (Global Health; Physical Functioning; Role/Social Limitations-Physical; Role/Social Limitations-Emotional/Behavioral; Bodily Pain/Discomfort; Behavior; Global Behavior Item; Mental Health; Self-Esteem; General Health Perception; Change in Health; Parental-Impact-Time; Parental Impact-Emotion; Family-Activities; Family-Cohesion) as measured by the CHQ-PF50 • Change from the baseline (Week 0) to the end of the double-blind withdrawal (DBW) period of radiographic images of the hands/wrists using modified Total Sharp Score (mTSS [van der Heijde method]; van der Heijde 2000; Ravelli et al. 2007) • Change from baseline (Week 0) to the end of the DBW in skeletal age based on hand/wrist radiograph and chronological age.

Abbreviations: DBW = double-blind withdrawal; JIA = juvenile idiopathic arthritis; OLLI = open-label lead-in.

5. Study Design

5.1. Summary of Study Design

Study I4V-MC-JAHV (JAHV) is a multicenter, randomized, double-blind, placebo-controlled, medication-withdrawal study with a safety/pharmacokinetic (PK) assessment period, an open-label lead-in (OLLI) period, and a double-blind withdrawal (DBW) period in patients with JIA who have had an inadequate response or intolerance to treatment with at least 1 other conventional or bDMARD. This includes patients with polyarticular JIA (rheumatoid factor positive or rheumatoid factor negative), extended oligoarticular course JIA, enthesitis-related JIA (ERA), and juvenile psoriatic arthritis (JPsA) as defined by the International League of Associations for Rheumatology (ILAR) criteria. The safety and tolerability data from this study are intended to establish an understanding of the benefit/risk relationship for baricitinib in patients with nonsystemic JIA.

Abbreviations: OLE = open-label extension; PediACR30 = Pediatric American College of Rheumatology 30 criteria; PK = pharmacokinetic(s); QD = once daily.

- Staggered approach to enrollment by age group (12 to <18 years, 9 to <12 years, 6 to <9 years, 2 to <6 years) will be implemented with older groups completing the safety/PK assessment period before younger groups are enrolled.
- Once the PK and safety profiles for an age group are confirmed, subsequent patients in that age group may enroll directly into the OLLI period. If the comparability assessment in the safety/PK period for an age group is inconsistent with baricitinib 4-mg exposures in adults with RA such that baricitinib dosage for the age group needs to be adjusted, the patients on the inconsistent dosage will discontinue the study and may enter the separate OLE study (JAHX).
- Patients who experience a disease flare during the DBW period will discontinue the study and may proceed directly to the separate OLE study (JAHX).

Figure JAHV.1. Study design for Clinical Protocol I4V-MC-JAHV.

5.2. Determination of Sample Size

A total of 128 patients will be randomized in a 1:1 ratio to baricitinib or placebo (64 per treatment arm) in the DBW period. This sample size will provide approximately 80% power to detect the difference in time to disease flare between the 2 treatment groups using a 2-sided test with a significance level of 0.05, assuming that the expected percentages of patients experiencing disease flare in the DBW period are 35% for baricitinib and 60% for placebo and that the dropout rate is no greater than 10% in this period.

It is estimated that 197 patients are required to enter the OLLI period to allow 128 patients to be randomized into the DBW period (assuming that 65% of the patients meet the Pediatric American College of Rheumatology (PedACR) 30 criteria at the end of the OLLI period). The nonresponder and dropout rate will be monitored during the OLLI period to adjust the overall sample size to ensure that a minimum of 128 patients will be randomized in the DBW. If the

PedACR30 response rate during the OLLI period is higher than the assumed rate of 65%, fewer than 197 patients may be required.

The above sample size and power estimates are based on nQuery[®]+nTerim 4.0.

5.3. Method of Assignment to Treatment

Patients who enter the PK lead-in period will be assigned a dose based on age. Doses of subsequent patients who enter the PK lead-in period may be adjusted until a dose is found that produces exposures within the range produced by baricitinib 4-mg in adults with RA. All patients who enter the OLLI period will receive a fixed age-based dose of baricitinib as determined in the PK lead-in period.

Patients who meet the PedACR30 response criteria at the end of the OLLI period will be randomized in a 1:1 ratio (baricitinib age-based dose or matching placebo) to double-blind treatment at Week 12. The randomization will be stratified by:

- history of prior bDMARD use (Yes versus No)
- the JIA categories (polyarticular and extended oligoarticular [combined] versus ERA and JPsA [combined])
- Predose exposure erythrocyte sedimentation rate (ESR) categories (elevated [>20 mm/hour] and not elevated) in the polyarticular JIA patients

Assignment to treatment groups will be determined by a computer-generated random sequence using an interactive web-response system (IWRS). The IWRS will be used to assign bottles containing double-blind investigational product to each patient. All patients <6 years of age will receive oral suspension. Patients ≥ 6 to <12 years old have the option of receiving the oral suspension. Patients >12 years will be supplied tablets only. Site personnel will enter the confirmation number found on the bottles into the IWRS, which confirms that they have located the correct bottles.

6. A Priori Statistical Methods

6.1. General Considerations

This plan describes *a priori* statistical analyses for efficacy, health outcomes, and safety that will be performed.

Statistical analysis of this study will be the responsibility of Eli Lilly and Company (Lilly). The statistical analyses will be performed using SAS® Version 9.4 or higher.

Not all displays described in this SAP will necessarily be included in the clinical study report (CSR). Not all displays will necessarily be created as a “static” display. Some may be incorporated into interactive display tools instead of or in addition to a static display. Any display described in this SAP and not included in the CSR would be available upon request.

Statistical tests of treatment effects and confidence intervals (CIs) will be performed at a 2-sided significance level of 0.05, unless otherwise stated.

Data collected at early termination visits will be mapped to the next scheduled visit number for that patient. For by-visit summaries, only visits in which a measure was scheduled to be collected will be summarized. Any unscheduled visit data will be included in the patient-level listings. However, the data might still be used in other analyses, including change from baseline to endpoint using last observation carried forward (LOCF) analyses and other categorical analyses.

6.1.1. Analysis Populations

For purposes of analysis, the following populations are defined based on the different treatment period as shown in [Table JAHV.6.1](#).

Table JAHV.6.1. Analysis Populations

	Population	Description
	Entered population	All participants who sign informed consent.
Efficacy Analysis population	Safety/PK population	All patients who received at least 1 dose of investigational product in the Safety/PK assessment period.
	OLLI population	All participants who take at least 1 age-based final dose, as confirmed by PK assessments of investigational product, in the OLLI period, other than the Safety/PK population.
	OLLI population 2	All patients who received at least 1 dose of investigational product in the OLLI period.
	Safety/PK and OLLI population	All enrolled patients who were initially assigned to the open-label investigational product in Safety/PK assessment period and OLLI period, following intent-to-treat (ITT) principles.
	DBW population	All randomized patients in the DBW period following intent-to-treat (ITT) principles.

	Population	Description
Safety Analysis population	DBW safety population	All randomized patients in the DBW period who receive at least 1 dose of investigational product.
	General safety population	All patients who received at least 1 dose of investigational product, which is baricitinib.

Abbreviations: DBW = doubleblind withdrawal; OLLI = open-label lead-in; PK = pharmacokinetic.

Efficacy analyses will be conducted by treatment periods with the corresponding analysis population, where the primary efficacy analysis will focus on the DBW period with the DBW population. Safety analyses will be performed by treatment periods with the corresponding safety population.

The patients who participate in the Safety/PK period and participate in the OLLI period with the age-based final dose will be eligible to participate in the DBW period if the patient is a PedACR30 responder at the end of the OLLI period. Thus, such patients from the Safety/PK assessment period will be included in the OLLI population 2 and DBW population. Also, Safety/PK assessment period and OLLI period may be combined for efficacy/safety analysis with the corresponding population that includes such patients.

In the rare situation where a patient is lost-to-follow-up at the first postbaseline visit but some safety data exist (e.g., unscheduled laboratory assessments) after first dose of study drug, a listing of the data or a patient profile will be provided.

6.1.2. Definition of Baseline and Postbaseline Measures

The baseline value for the efficacy (except flare), health outcomes is defined as the last non-missing measurement on or prior to the date of first study baricitinib administration. For patients who participate in the Safety/PK period, this value will be recorded on or before Visit 2 (Day 1); for the other patients who started with the OLLI period, this value will be recorded on or before Visit 5 (Week 0).

The baseline value for disease flare analyses is defined as the last non-missing measurement on or prior to the date of randomization (beginning of the DBW period). This value will be recorded on or before Visit 9 (Week 12).

Baseline for the safety analyses is defined in Section 6.18. Postbaseline measurements are collected after study drug administration through Visit 17 (Week 44) or early discontinuation visit. For data collected in the electronic Clinical Outcomes Assessment (eCOA) tablet (including Patient-Reported Outcomes [PRO] and Clinician-Reported Outcomes [ClinRO]) and related to efficacy assessments, unscheduled postbaseline visits that fall within the visit windows defined by Lilly will be summarized in the by-visit analyses if there is no scheduled visit available. Refer to clinical protocol I4V-MC-JAHV(d) for detail of the visit windows. If there is more than 1 unscheduled visit within the defined visit window and no scheduled visit is available, the unscheduled visit closest to the scheduled visit date will be used. If 2 unscheduled visits of equal distance are available, then the latter of the 2 will be used.

Postbaseline measures for the safety analyses are defined as the nonmissing scheduled (planned) measurements after the date of first study drug administration for continuous measures by-visit analyses and all nonmissing measurements after the date of first study drug administration for all other analyses.

6.1.3. Definition of OLLI and DBW Analysis Periods

The OLLI period starts at:

- The completion of Safety/PK assessment period for Safety/PK population patients
- The time of first age-based dose of baricitinib for OLLI population patients

The OLLI period ends for the following study events:

- Week 12 (Visit 9) for patients who do not meet the randomization criteria, or
- Visit of early discontinuation of study treatment in the OLLI period.

The DBW period starts at the time of randomization and ends at the following study events:

- Patient experience disease flare (defined in [Table JAHV.6.4](#))
- Week 44 (Visit 17) for patients who do not flare, or
- Visit of early discontinuation of study treatment in the randomized double-blind withdrawal period.

6.1.4. Analysis Methods

The primary endpoint will be the time-to-flare during the DBW period for randomized patients. Patients who discontinue or complete the DBW period without experiencing a flare will have their data censored at the time of their discontinuation date or completion date. The censored patients will contribute to the at-risk set in the stratified logrank test. Survival curves will be estimated using the Kaplan–Meier method in the DBW period. Treatment comparisons will be performed using a stratified log-rank test across JIA categories (polyarticular and extended oligoarticular [combined] versus ERA and JPsA [combined]) for the DBW population in the DBW period. Treatment comparisons may also be analyzed using a Cox proportional hazards model adjusted for stratification variables. The hazard ratio with 95% CIs will be reported. And the similarity of treatment effect across JIA categories (polyarticular and extended oligoarticular [combined] versus ERA and JPsA [combined]) will be evaluated using Cox proportional hazards regression adjusted for stratification variables. If any of these variables are redundant for a particular model, they will be dropped.

Secondary efficacy and health outcomes analyses ([Table JAHV.6.4](#) and [Table JAHV.6.5](#)) will be based on treatment period and respective study populations.

Efficacy, health outcomes, and safety data collected in OLLI period will be summarized without inferential statistics.

In the DBW period, the main analysis of categorical efficacy variables and health outcomes variables will use a logistic regression analysis with treatment, JIA categories (polyarticular and extended oligoarticular [combined] versus ERA and JPsA [combined]), predose exposure ESR categories (elevated [>20 mm/hour] and not elevated), history of prior bDMARD use (Yes or No) as covariates in the model. The p-value and 95% CI for the odds ratio from the logistic regression model are used for statistical inference.

In the DBW period, the main analysis for all continuous efficacy and health outcomes variables will use analysis of covariance (ANCOVA) model with treatment, JIA patient categories (polyarticular and extended oligoarticular [combined] versus ERA and JPsA [combined]), predose exposure ESR categories (elevated [>20 mm/hour] and not elevated), history of prior bDMARD use (Yes or No), and baseline score as covariates in the model. For ESR and high-sensitivity C-reactive protein (hsCRP) analysis, predose ESR level categories will not be included as a covariate. Type III sums of squares for the least-squares mean (LSM) will be used for the statistical comparison of treatment groups, and the LSM difference, standard error, p-value and 95% CI will also be reported. The LOCF approach will be used to impute missing data.

The mixed model repeated measures (MMRM) analysis will also be considered as a supplemental analysis method. The MMRM will use a restricted maximum likelihood (REML) estimation. The model will include treatment, JIA patient categories (polyarticular and extended oligoarticular [combined] versus ERA and JPsA [combined]), predose exposure ESR categories (elevated [>20 mm/hour] and not elevated), history of prior bDMARD use (Yes or No), visit, treatment-by-visit-interaction, baseline score and baseline-by-visit-interaction as fixed effects. If any of these are redundant for a particular model, they will be dropped. An unstructured (co)variance structure will be used to model the between- and within-patient errors. If this analysis fails to converge, the heterogeneous autoregressive [ARH(1)], followed by the heterogeneous compound symmetry (CSH), followed by the heterogeneous Toeplitz (TOEPH) will be used. The Kenward-Roger method will be used to estimate the degrees of freedom. Type III tests for the LSM will be used for the statistical comparison. The LSM difference, standard error, p-value, and 95% CI will also be reported.

The primary safety analysis will be conducted during the DBW period for the DBW safety population. Fisher's exact test will be used for the adverse events (AEs), discontinuation, and other categorical safety data for between-treatment group comparisons. Continuous vital signs, body weight, and other continuous safety variables, including laboratory variables will be analyzed by an ANCOVA with treatment group and baseline value in the model. The significance of within-treatment group changes from baseline will be evaluated by testing whether or not the treatment group LSM changes from baseline are different from zero; the standard error and within-group p-value for the LSM change will also be displayed. In addition, the LSM difference between baricitinib and placebo groups, the corresponding p-value, and 95% CI will be provided. Treatment-emergent high/low for categorical laboratory safety analyses will also be produced.

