10.3.3.2. Secondary Analyses

Secondary efficacy and health outcomes analyses ([Table JAHV.8](#)) will be based on the following study periods and study populations:

- OLLI period population: All participants who take at least 1 age-based final dose as confirmed by PK assessments of investigational product in the OLLI period, other than the Safety/PK population. Baseline is defined as Week 0.
- DBW period population: All randomized patients in DBW period following intent-to-treat (ITT) principles.

Table JAHV.8. Secondary Efficacy Endpoint Analyses

Endpoint	Population	Analysis Period	Treatment Comparisons	Analysis Method
Proportion of disease flare	DBW	Week 16 to Week 44	Baricitinib versus placebo	Logistic regression with NRI
PedACR core set variables: change from baseline	OLLI	Week 2 to Week 12	No comparison	Summary statistics
	DBW	Week 16 to Week 44	Baricitinib versus placebo	ANCOVA with LOCF
PedACR30/50/70/90/100 response rates (compare to patient's condition prior to first dose of investigational product)	OLLI	Week 2 to Week 12	No comparison	Summary statistics
	DBW	Week 16 to Week 44	Baricitinib versus placebo	Logistic regression with NRI
PhS and PsS scores (CHQ-PF50): change from baseline	OLLI	Week 2 to Week 12	No comparison	Summary statistics
	DBW	Week 16 to Week 44	Baricitinib versus placebo	ANCOVA with LOCF
Parental Impact –Time/Emotion scores (CHQ-PF50): change from baseline	OLLI	Week 2 to Week 12	No comparison	Summary statistics
	DBW	Week 16 to Week 44	Baricitinib versus placebo	ANCOVA with LOCF
Inactive disease: proportion	OLLI	Week 2 to Week 12	No comparison	Summary statistics
	DBW	Week 16 to Week 44	Baricitinib versus placebo	Logistic regression with NRI
Minimal disease activity: proportion	OLLI	Week 2 to Week 12	No comparison	Summary statistics
	DBW	Week 16 to Week 44	Baricitinib versus placebo	Logistic regression with NRI
Remission: proportion	DBW	Week 28 to Week 44	Baricitinib versus placebo	Logistic regression with NRI
JADAS-27: change from baseline	OLLI	Week 2 to Week 12	No comparison	Summary statistics
	DBW	Week 16 to Week 44	Baricitinib versus placebo	ANCOVA with LOCF
Pain severity VAS (CHAQ): change from baseline	OLLI	Week 2 to Week 12	No comparison	Summary statistics
	DBW	Week 16 to Week 44	Baricitinib versus placebo	ANCOVA with LOCF

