Measure	Description	Variable	Derivation/Comment	Imputation Approach if with Missing Components
Disease remission	Remission is defined as inactive disease for at least 24 consecutive weeks (Wallace et al. 2011). In inactive disease as secondary endpoint, ESR measure is used as acute-phase reactant in the core criteria. Thus, the disease remission as secondary endpoint is based on ESR.	Proportion of patients who achieved minimal disease activity	
 At Visit 13, check if there are inactive disease status in all Visit 7, Visit 8, Visit 9, Visit 10, Visit 11, Visit 12, if yes, conclude the patient has achieved disease remission status. At Visit 14, check if there are inactive disease status at Visit 8, Visit 9, Visit 10, Visit 11, Visit 12, Visit 13, if yes, conclude the patient has achieved disease remission status. At Visit 15, check if there are inactive disease status at Visit 9, Visit 10, Visit 11, Visit 12, Visit 13, Visit 14, if yes, conclude the patient has achieved disease remission status. At Visit 16, check if there are inactive disease status at Visit 10, Visit 11, Visit 12, Visit 13, Visit 14, Visit 15, if yes, conclude the patient has achieved disease remission status. At Visit 17, check if there are inactive disease status at Visit 11, Visit 12, Visit 13, Visit 14, Visit 15, Visit 16, if yes, conclude the patient has achieved disease remission status. 	Missing if item is missing. NRI will be applied to missing data.

Secondary Efficacy Endpoint Analyses

Measure	Description	Variable	Derivation/Comment	Imputation Approach if with Missing Components

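### Binary efficacy endpoints in the withdrawal period rest on logistic regression with no named test and no rule for sparse or separated data

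*SAP*

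**What the plan says.** SAP 6.1.4 sets one main analysis for categorical efficacy and health-outcome variables in the DBW period: logistic regression with treatment, JIA category, pre-dose ESR category and prior bDMARD use. It then states: "The p-value and 95% CI for the odds ratio from the logistic regression model are used for statistical inference". Protocol 10.3.3.2 (Table JAHV.8) assigns "Logistic regression with NRI" to PedACR30 to 100, inactive disease, minimal disease activity, remission and the proportion with flare.

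On implementation, SAP 6.1 says "Statistical tests of treatment effects and confidence intervals (CIs) will be performed at a 2-sided significance level of 0.05" and "The statistical analyses will be performed using SAS" (version 9.4 or higher), with no procedure options. Neither document says whether the p-value is Wald, score or likelihood-ratio, or how the model is to be estimated.

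Fallbacks exist elsewhere. SAP 6.1.4 gives the MMRM an ordered list of covariance structures if it fails to converge, and uses Fisher's exact test for categorical safety data. The rule in SAP 6.2 for dropping redundant terms concerns adjustment variables, not separation on treatment.

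The strictest endpoint is remission. SAP Table JAHV.6.4 says "Remission is defined as inactive disease for at least 24 consecutive weeks", and its derivation requires inactive disease at six consecutive earlier visits, the first qualifying visit being Visit 13. Under SAP 6.3.2, missing visits count as non-response.

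**The concern.** When one arm has no responders, the treatment term is separated: the likelihood rises without limit as the log odds ratio grows, so no finite maximum-likelihood estimate exists. Software stops at some iteration and prints a large coefficient with a far larger standard error. A Wald p-value from that fit is close to 1 however many responders the other arm has, and the Wald interval is unusable. The most extreme contrast then yields the least informative result.

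The ingredients are present. Inactive disease needs several conditions at once (no active joints, physician global of 0, ESR not above 20, and others), remission needs it to persist, patients leave at flare, and planned flare is "35% for baricitinib and 60% for placebo". At stake are the reported odds ratios and p-values of a few secondary endpoints, and the choice of a substitute method after the data are seen.

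**Working it through.** **1. The plan's own figure.** SAP 5.2 states "approximately 80% power to detect the difference in time to disease flare" with 64 patients per arm. Hazard ratio = ln(0.65)/ln(0.40) = 0.470. Freedman events = (1.960 + 0.842)² × (1.470/0.530)² ≈ 61. Mean flare proportion = (0.35 + 0.60)/2 = 0.475, and 61/0.475 = 128.4. So 128 patients reproduces. The calculation concerns time to flare only; no rate or power is stated for any other binary endpoint. Non-responder imputation keeps the denominator at 64 per arm.

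**2. Chance of an empty placebo cell.** P(0 of 64) = (1 − p)^64, with p assumed:

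| Placebo rate | 1% | 2% | 3% | 5% | 10% |
|---|---|---|---|---|---|
| P(0/64) | 53% | 27% | 14% | 4% | 0.1% |

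**3. What each method returns.** Unadjusted, baricitinib versus placebo:

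| Table | Wald p | Likelihood-ratio p | Fisher p | Firth p |
|---|---|---|---|---|
| 6/64 v 0/64 | near 1 | 0.003 | 0.028 | 0.011 |
| 8/64 v 0/64 | near 1 | 0.0007 | 0.006 | 0.0025 |
| 10/64 v 0/64 | near 1 | 0.0001 | 0.0013 | 0.0005 |
| 10/64 v 1/64 | 0.021 | 0.002 | 0.009 | 0.004 |

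The Wald value depends on where iteration stops. For 10 versus 0 it is 0.90 with a limit of 12 iterations, 0.972 with 15 and 0.997 with 20; two standard routines run to their own stopping rules gave 0.996 and 0.999. Adding three simulated binary covariates changes little: for 8 versus 0 the Wald p is 0.995 and Firth 0.0043. Firth also gives a finite odds ratio; unadjusted for 8 versus 0 it is (8.5 × 64.5)/(56.5 × 0.5) = 19.4.

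**4. Power and size.** These come from summing binomial probabilities over all tables with 64 per arm, unadjusted, counting Wald as non-significant when a cell is empty:

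| True rates | Wald | Fisher |
|---|---|---|
| 10% v 1% | 12.6% | 44.7% |
| 15% v 2% | 46% | 69% |
| 20% v 5% | 69% | 67% |
| 30% v 10% | 82% | 77% |

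Firth power at 10% versus 1% is 58.9%. With equal rates of 2% and 5%, the likelihood-ratio test rejects 7.6% and 7.9% of the time against a nominal 5%; Firth rejects 0.5% and 2.9%.

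**5. A cell that is empty by construction.** SAP Table JAHV.6.7 lists a baricitinib-placebo logistic regression of hsCRP-based remission at Weeks 16, 32 and 44. Table JAHV.6.6 uses the same derivation logic as the ESR version, which first allows remission at Visit 13. The Schedule of Activities places Visit 13 at Week 28 and Visit 10 at Week 16, and protocol Table JAHV.8 also starts remission at Week 28. At Week 16 both arms have zero remissions and the model cannot be fitted. Penalisation would return an odds ratio of about 1 with no information in it.

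**The case against.** A reader might infer that the SAP prescribes a maximum-likelihood Wald test that yields one particular p-value, such as 0.97. The documents do not support that. The SAP names neither Wald nor maximum likelihood for this model, and any such value is an artefact of the stopping rule. The likelihood-ratio test of the same model does not fail: 0.0007 for 8 versus 0, with power of about 75% at 10% versus 1%. This stands, but the test is not specified, it is liberal in sparse data, so part of that power comes from inflated size, and it leaves the odds ratio infinite.

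Rarity is also assumed. Only PedACR30 responders are randomised; DBW PedACR response is judged against the state before first dose; about 26 of 64 placebo patients (40%) are planned not to flare; analyses begin four weeks after withdrawal; and early remission assessments count open-label visits. All of this works against an empty placebo arm, and at a 10% rate the chance is 0.1%. A single placebo responder restores a usable Wald test, and by 20% versus 5% Wald is no worse than Fisher. The concern therefore does not extend to flare proportion or PedACR30.

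Nor does it follow that the trial would report no difference: protocol 10.3.1 also has proportions with 95% confidence intervals reported, so the contrast would be visible beside the failed odds ratio. The endpoints are secondary, with no multiplicity control (SAP 6.5).

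**Conclusion.** The gap is real and narrow. SAP 6.1.4 makes a logistic-regression p-value and odds-ratio interval the basis of inference for all DBW binary efficacy endpoints without naming the test or providing for sparse or separated data. If a strict endpoint has no placebo responders, the odds ratio and its Wald interval are not estimable and a default Wald p-value lies at about 0.90 to 0.999, where Firth gives 0.0025 for 8/64 versus 0/64.

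How likely this is rests on assumed placebo rates: more likely than not at about 1%, small by 5%, negligible at 10%. The figures in the tables are unadjusted, whereas the planned model has three covariates. The loss is confined to sparse secondary endpoints, and the primary stratified log-rank test is untouched. This is a cheap improvement, not a threat to the trial's main conclusion. The Week 16 hsCRP-remission entry is a plain error that depends on no assumed rate.

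**What to change.** In SAP 6.1.4, state that the same covariate-adjusted model is fitted by Firth penalised likelihood, with profile-penalised confidence intervals and penalised likelihood-ratio p-values, for the sparse endpoints named in advance (remission, inactive disease, PedACR90 and PedACR100) and for any other binary efficacy endpoint with an empty treatment-by-response cell. State the test type for the remaining endpoints.

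A switch to Fisher's exact test whenever a cell falls below 5 is not recommended: it discards the covariate adjustment and would trigger where the ordinary model still works, as in 10/64 versus 1/64.

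In Table JAHV.6.7, delete Week 16 from the hsCRP-remission comparison.

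The cost is a sentence or two, one procedure option and one table entry. The downside is that penalised odds ratios shrink slightly towards 1.
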